Diagnosis and Main Inclusion/Exclusion Criteria	
Inclusion criteria:
 
 
1. Biallelic pathogenic or likely pathogenic variants in PMM2 OR Biallelic variants of uncertain significance, pathogenic, or likely pathogenic variants in PMM2 AND Enzymatic confirmation of PMM2 enzyme deficiency
 
2. Age <math>\geq 4</math> years old, and
 
3. Affected with ataxia evidenced by mini International Cooperative Ataxia Rating Scale (Mini-ICARS) score <math>>0</math> at baseline.
 
 
Exclusion criteria:
 
 
1. Hepatic impairment defined as AST/ALT <math>>3.0 - 5.0 \times</math> ULN if baseline was normal; <math>>3.0 - 5.0 \times</math> baseline if baseline was abnormal
 
2. Renal impairment defined as serum creatinine 1.5-1.9 times ULN for age OR <math>\geq 26.5 \text{ umol/l}</math> increase from ULN for age
 
3. Hypokalemia
 
4. Hyponatremia
 
5. Hyperchloremic acidosis
 
6. Adrenal insufficiency
 
7. Hypersensitivity to acetazolamide
 
8. Hypersensitivity to any of the components of the placebo
 
9. History of treatment with experimental drug within 28 days of Visit 1
 
10. Currently taking Mecamylamine, Sodium Phosphates, Salicylates, Mefloquine, Methenamine and other Carbonic Anhydrase Inhibitors
 
11. Weight <math><10 \text{ kg}</math>
 

Study Product, Dose, Route, Regimen	
Acetazolamide or Placebo
 
Acetazolamide capsules <math>\leq 30 \text{ mg/kg/day}</math> divided BID or matching placebo, divided BID daily, by mouth.
 
Due to the potential of subject intolerance, we will start patients on a lower dose divided BID and titrate up in a stepwise manner per table 1 if well tolerated with no AEs or abnormal pH. If the pH is <math><7.3</math> and/or bicarbonate <math><21</math>, the dose will be reduced by <math>7\text{mg/kg/day}</math>.

Duration of Administration	12 months (52 weeks) total, 6 months (26 weeks) blinded, 6 months (26 weeks) open label extension
Reference therapy	Placebo

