Acetazolamide is an FDA-approved drug for adults for treatment of glaucoma, epilepsy, altitude sickness, and edema. FDA approved doses are in adults 250 to 1000 mg/day divided once to four times daily. A documented off-label use is for treatment of familial periodic paralysis. While the regular-release capsule is not FDA approved in children, it is used commonly in clinical practice and recommended doses have been established in children for management of glaucoma and seizures, reversal of metabolic alkalosis, and prevention and treatment of altitude sickness at 10-30 mg/kg/day given in one to four divided doses. The extended released capsule is FDA-approved in children with a max dose of 30 mg/kg/day or 1000 mg/day (Acetazolamide, 2020).

Acetazolamide is contraindicated in cases of marked liver disease or dysfunction and in patients with cirrhosis because of the risk of development of hepatic encephalopathy and electrolyte imbalance. It is also contraindicated in patients with severe renal disease as it may potentiate acidosis and may cause CNS adverse effects in dialysis patients. It is contraindicated for individuals with carbonic anhydrase inhibitor hypersensitivity, sulfonamide hypersensitivity, electrolyte disturbances, and adrenal insufficiency. It has been reported to occasionally induce

bone marrow suppression and blood dyscrasias. It is an FDA pregnancy risk category C. These contraindications are reflected in our study exclusion criteria.

In this study, regular-release acetazolamide will be dispensed in compounded capsule and compounded liquid formulations.

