## 1.5 Risks and Benefits

### Risks

In general, acetazolamide is considered a safe drug. Per the package insert, severe adverse reactions that have been reported with administration of acetazolamide include seizures, muscle paralysis, hepatic necrosis, hepatic failure, hepatic encephalopathy, toxic epidermal necrosis, agranulocytosis, anaphylaxis, aplastic anemia, hemolytic anemia, Stevens-Johnson syndrome, pancytopenia, acute generalized exanthematous pustulosis, renal failure, and renal tubular obstruction. The incidence of each reaction is unknown. It is likely that individuals who have significant baseline allergy to acetazolamide and other components, hepatic dysfunction, blood dyscrasias, and/or renal dysfunction would be at higher risk for these severe reactions. Thus we are assessing for hepatic dysfunction, renal dysfunction, allergy, and blood dyscrasias at baseline and excluding individuals with significant disturbances in their laboratory assessments or have a history of allergy to the components of the therapeutic agent or placebo (as defined by the exclusion criteria below). We will monitor complete blood count (CBC), liver function tests (LFT), venous blood gas (VBG or bicarbonate/CO2), electrolytes, and creatinine, and urinalysis with urine creatinine, calcium, and protein at baseline and regularly throughout the study, and if any individual meets exclusion criteria at any point during the study, we will terminate their treatment. Patients may develop acidosis on acetazolamide therapy, which may lead to inability to continue the therapy longer or a decrease in dosage. Acetazolamide has been associated with growth suppression in pediatric patients, although not all individuals have been reported to have poor growth and the dosages associated with growth suppression have not been consistent. Growth has been reported to resume and improve after discontinuation of acetazolamide. We will monitor growth parameters (height, weight, head circumference) regularly throughout the study and tailor their management and continuation in the study on a case by case basis. We will monitor patients' acid/base status and titrate acetazolamide accordingly. We will also obtain a one-time measurement of acetazolamide serum concentration at steady state at the six-month visit.

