### **Objective 3 (Secondary):**

**To examine the effect of acetazolamide on PMM2 biomarkers including carbohydrate deficient transferrin, electrolytes (Na, K, Cl, CO2), VBG (pH, pCO2, PO2, CO2, Base excess) or bicarbonate/CO2, liver function tests (AST, ALT, GGT, indirect and direct bilirubin, total protein, albumin, alkaline phosphatase), kidney function tests (BUN, Creatinine, Urinalysis, urine calcium/creatinine ratio, urine protein/creatinine ratio), growth (height, weight, head circumference), vital signs (blood pressure, respiratory rate, heart rate), PROMIS scores, dysarthria using the PATA score, and NPCRS score.**

We will collect these data at baseline and after 6 months of placebo or treatment and identify changes from baseline. We will analyze if there is a difference of changes between the treatment and placebo group. We will also compare baseline measurements to the last measurement obtained as part of the open label extension and determine if there are changes to these measurements.

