### **3 Study Design**

#### **3.1 General Description**

This study is a double-blind, placebo-controlled, 1:1 randomized clinical therapeutic trial of acetazolamide for the treatment of ataxia in patients with PMM2-CDG. Clinical history and screening data will be reviewed to determine subject eligibility. Potential subjects who have biallelic pathogenic or likely pathogenic variants in PMM2 OR biallelic variants of uncertain significance, pathogenic, or likely pathogenic variants in PMM2 AND Enzymatic confirmation of PMM2 enzyme deficiency will be consented. Baseline data will be collected prior to randomization and at treatment initiation. Subjects who meet all inclusion criteria and none of the exclusion criteria will be enrolled into the study. Each subject who meets all the inclusion and none of the exclusion criteria will then be randomized to placebo or acetazolamide. They will be administered weight-dependent doses of acetazolamide or an equivalent dose of placebo twice daily by mouth. Initial dose of acetazolamide is at least 7.58 mg/kg/day per Table 1 . If the pH is <7.3 and/or bicarbonate <21, a value associated with mild metabolic acidosis, the dose will be reduced per table 1. Subjects will be randomized after Visit 1, will initiate blinded therapy within the first week, and will continue on prescribed/adjusted blinded treatment until Visit 4. Of note, the volume or number of capsules will be adjusted based on tolerance as assessed by symptoms and laboratories. If an individual is randomized to the placebo arm, the initial number of capsules will be as per Table 1, and number of capsules will also be adjusted based on symptoms and laboratory values each time dose adjustment is planned. Open label period will then begin after Visit 5 up to Visit 9 (see Figure 1 and Table 3). As both the subject and investigator do not know if the subject received placebo or acetazolamide, the dose of acetazolamide will be started at Visit 5 per table 1 and titrated upwards in the same manner in Visits 6, 7 and 8 (remote) as in Visits 2, 3 and 4 (remote). Subjects will have the option to withdraw from the study any time after Visit 5 if they do not wish to proceed onto or continue with the open label phase.

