### 4.2 Exclusion Criteria

- Hepatic impairment defined as AST/ALT >3.0 - 5.0 x ULN if baseline was normal; >3.0 - 5.0 x baseline if baseline was abnormal in the last 12 months
- Renal impairment defined as serum creatinine 1.5-1.9 times ULN for age OR  $\geq 26.5$  umol/l increase from ULN for age
- Hypokalemia
- Hyponatremia
- Hyperchloremic acidosis
- Adrenal insufficiency
- Hypersensitivity to acetazolamide
- Hypersensitivity to any of the components of the placebo
- History of treatment with experimental drug within 28 days of Visit 1
- Currently taking Mecamylamine, Sodium Phosphates, Salicylates, Mefloquine, Methenamine, other Carbonic Anhydrase Inhibitors, Phenytoin, Primidone, folic acid antagonists, antidiabetic agents, quinidine, lithium, cyclosporine, sodium bicarbonate.

- Participation in another therapeutic trial - the subject will not be permitted to participate in any other drug trial during the blinded phase and during the 28 days prior to Visit 1
- Pregnant (positive urine beta-HCG test) or nursing (by history) women
- Weight <10 kg

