### Subject Identification:

Ethical and confidential research standards will be maintained. The minimum necessary protected health information will be used in study records. Computer records of data will be password protected behind institutional information technology security firewalls. All information will be treated with strict adherence to professional standards of confidentiality.

The following is a detailed list of study visits from screening to final follow-up and the required procedures/tests.

### 6.1 Visit 1 – Week 0

- Screening for eligibility
- Informed consent; no procedures will occur until informed consent and eligibility criteria are confirmed.
- Interview elements:
  - Medical history (past and current medical conditions, past surgical history)
  - Clinical history (history of present illness, any assessments)
  - Concomitant medication review
  - Ongoing therapies (physical therapy (PT), occupational therapy (OT), speech therapy (ST), feeding therapy (FT))
- Procedural elements:
  - Physical exam: Vital signs – temperature, systolic and diastolic blood pressures (mmHg), heart rate (beats/minute), respiratory rate (breaths/minute), Growth Data\* - length/height (cm), weight (kg), head circumference (HC in cm), Exam by systems – (normal/abnormal) brief neurologic exam, cardiovascular exam,

- abdominal exam, (HEENT) head ears eyes nose throat exam, dermatologic exam, pulmonary exam, musculoskeletal exam
- Mini-ICARS
- PATA
- NPCRS
- Blood collection\*\* (CBC (WBC, Hgb, Hct, Plt, % Neutrophils, % Lymphocytes, % Eosinophils, % Basophils, % Monocytes, % Bands, MCV, MCHC, MCH), electrolytes (Na, K, Cl, CO2), VBG (pH, pCO2, PO2, CO2, Base excess) or bicarbonate/CO2, liver function tests (AST, ALT, GGT, indirect and direct bilirubin, total protein, albumin, alkaline phosphatase, calcium, phosphorus, vitamin D, parathyroid hormone), coagulation factors (prothrombin time, coagulation factor XI, and antithrombin) kidney function tests (BUN, Creatinine), CTX, BSAP
- Urine collection (Urinalysis, urine calcium/creatinine ratio, urine protein/creatinine ratio, HCG for females)
- Survey given to families to complete and returned to site at or after visit by mail or electronically
  - PROMIS
- Performed after visit once inclusion and exclusion criteria are met and Mini-ICARS score established
  - Randomization

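### The hepatic entry criterion has no upper limit for a patient whose AST/ALT was already abnormal, so a stable elevation of any size passes

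*Combined protocol and SAP*

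**What the plan says.** The hepatic exclusion in Section 4.2 has two limbs. If baseline AST/ALT was normal, the limit is 3.0 - 5.0 times ULN. If it was abnormal, the patient is excluded when the value is ">3.0 - 5.0 x baseline if baseline was abnormal in the last 12 months". The Study Summary gives the same two limbs, but its second ends at "baseline if baseline was abnormal", with no 12-month window. Neither place says which measurement baseline is. Neither list has another liver criterion: nothing on cirrhosis, bilirubin, albumin or history of liver disease, and no exclusion at the investigator's judgement.

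Section 3.1 makes the list decisive: "Each subject who meets all the inclusion and none of the exclusion criteria will then be randomized to placebo or acetazolamide".

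Section 1.2 gives the clinical background: "Acetazolamide is contraindicated in cases of marked liver disease or dysfunction and in patients with cirrhosis". The same paragraph ends: "These contraindications are reflected in our study exclusion criteria".

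Sections 8.1 and 8.5 reuse the two limbs as an adverse-event definition and as a rule for stopping drug.

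**The concern.** An entry criterion for hepatic impairment should respond to how impaired the liver is at entry. The second limb responds only to change. It suits on-study monitoring, which is its role in Sections 8.1 and 8.5. At entry it cannot detect an elevation that was already present and has not moved.

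What is at stake is participant safety and the protocol's account of its own safeguards. Section 1.5 lists hepatic necrosis, hepatic failure and hepatic encephalopathy among the reported severe reactions, and considers patients with hepatic dysfunction likely to be at higher risk. Participants may be as young as 4 years. The sample size and the primary analysis are not affected.

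**Working it through.** **Inputs.** From Section 4.2: the limit L, written as a range from 3.0 to 5.0, and the two limbs. The documents give no enzyme levels for this population, so the levels below are hypothetical, in multiples of ULN. The plan states no figure on this point to reproduce.

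**Rule.** Let b be the baseline value and s the value tested at entry.
- Baseline normal (b ≤ 1): compare s with L.
- Baseline abnormal (b > 1): compare s/b with L.

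L can be read in three ways: exclude above 3.0, exclude above 5.0, or (literally) exclude only within the band above 3.0 and up to 5.0.

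**Baseline read as an earlier record.**

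| Earlier → now (x ULN) | Quantity tested | Above 3.0 | Above 5.0 | Band |
|---|---|---|---|---|
| 4 → 4 | 4/4 = 1.0 | admitted | admitted | admitted |
| 8 → 8 | 8/8 = 1.0 | admitted | admitted | admitted |
| 3 → 8 | 8/3 = 2.67 | admitted | admitted | admitted |
| 2 → 8 | 8/2 = 4.0 | excluded | admitted | excluded |
| normal → 3.5 | 3.5 | excluded | admitted | excluded |
| normal → 5.5 | 5.5 | excluded | excluded | admitted |

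The two stable rows are admitted in every column. With threshold L, the highest admitted value for an abnormal earlier value b is L x b. For b = 2 that is 3 x 2 = 6 to 5 x 2 = 10 x ULN, and it rises without limit as b rises.

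**Baseline read as the Visit 1 value.** If the value tested at entry is also the Visit 1 value, then s/b = 1.0 for everyone with an abnormal baseline and the second limb can never be met. The earlier-to-now rows do not apply on this reading, but the result for a stable elevation is the same.

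**Does anything else close the gap at entry?** Section 1.5 says significant laboratory disturbances are excluded, but only as the exclusion list defines them, so it leads back to Section 4.2. By contrast, the renal criterion in the same list is tied to ULN for age for every patient.

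**On study.** The numeric stop in Section 8.5 uses the same ratio. If baseline is the Visit 1 value (an assumption), a patient entering at 4 x ULN reaches it only above 3 x 4 = 12 to 5 x 4 = 20 x ULN. If baseline is an earlier record of 3 x ULN, it is reached above 9 to 15 x ULN.

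**The case against.** The strongest reply is that a limb relative to baseline may be deliberate. Section 2, Objective 3 lists "liver function tests (AST, ALT, GGT, indirect and direct bilirubin, total protein, albumin, alkaline phosphatase" and other measures among the PMM2 biomarkers, the disease is multisystemic, and the trial needs 26 evaluable patients. How much chronic elevation to tolerate is a clinical judgement. This stands as a reason not to exclude every raised value. But no section states the intention, and tolerating chronic elevation does not require having no ceiling.

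The second reply is that other safeguards exist. Liver tests are drawn at Visit 1 and repeated at Visits 2 to 4 (Sections 6.1 to 6.4), clinical interpretation of laboratory values is recorded (Section 3.7), treatment may be paused (Section 4.3), significant changes prompt re-evaluation (Section 8), and the numeric stop brings in the DSMB (Section 8.5). These lessen the consequence. The on-study measures act only after dosing has begun, and no entry criterion tells an investigator to decline a stable high value.

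Two stronger readings are tempting, and the documents do not support them.

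- A reader might infer that the rule admits patients for whom the drug is contraindicated. Section 1.2 does not mention AST/ALT levels, and nothing in the documents equates a raised enzyme with the liver disease named there. A patient stable at 8 x ULN is not thereby shown to be contraindicated.
- A reader might infer that a stable 8 x ULN is admitted while a new 5.5 x ULN is always refused. That holds at either threshold (3.0 or 5.0). On the literal band reading the new 5.5 x ULN is not excluded either.

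**Conclusion.** The point holds in this form: for a patient with an abnormal baseline, the only hepatic criterion at entry tests the rise over baseline, so a stable elevation is never excluded at any level. The result does not depend on how baseline or the 3.0 - 5.0 limit is read. The criterion therefore does not ensure that the liver contraindication in Section 1.2 is reflected in the exclusions.

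The practical size is unknown. AST/ALT is a proxy, the number of patients with raised enzymes is not given, and monitoring mitigates part of the risk once treatment starts. The gap in the text is certain. That any particular patient would be harmed is not shown. It is worth correcting because the change is small and uses a test already scheduled.

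**What to change.** 1. In Section 4.2 and the Study Summary, add an exclusion: *AST or ALT above 5 x ULN at Visit 1, before randomization, whatever the earlier value.* The figure 5 is the upper number already in the criterion. Nothing in the documents ties it to the contraindication, so the clinical lead should confirm it after the sites count known patients above it. The new line also closes the gap above 5 x ULN that the band wording leaves for newly raised values.
2. Define baseline: in Section 4.2 and the Summary, the earlier record from the last 12 months; in Sections 8.1 and 8.5, the Visit 1 value.
3. Section 1.5 says "if any individual meets exclusion criteria at any point during the study, we will terminate their treatment". For liver tests, point this sentence to the stop-and-restart rule in Sections 8.1 and 8.5. Otherwise the new ceiling would end treatment for a patient drifting from 4.9 to 5.1 x ULN, a ratio of 5.1/4.9 = 1.04.

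**Effect.** The 8 → 8 and 3 → 8 patients become ineligible (8 > 5) and the 4 → 4 patient stays eligible. With baseline set to the Visit 1 value, the highest possible on-study numeric stop becomes 3 x 5 = 15 to 5 x 5 = 25 x ULN instead of unlimited.

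**Cost.** A few lines of text and no new procedure: Visit 1 already includes the liver tests, and Section 6.1 lists randomization under "Performed after visit once inclusion and exclusion criteria are met and Mini-ICARS score established". Patients with chronic elevation above 5 x ULN are lost to a trial that needs 26 evaluable patients, which is why the site count comes first.

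**What it leaves open.** An enzyme ceiling does not identify cirrhosis; the clinical lead should decide whether that needs its own line. Between 3 and 5 x ULN, stable and new elevations would still be treated differently if the limit is read as above 3.0 or as a band.

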#### 4.3 Subject Recruitment, Enrollment and Screening

- Patients seen clinically by genetics at Seattle Children's, CHOP, and Mayo Clinic with molecularly and/or enzymatically-confirmed diagnosis of PMM2-CDG will be approached for consent. Additional patients may be consented if referred by an external provider to the genetics clinic. If an individual fails screening, they can be rescreened 4 or more months after their initial screening. Subjects' treatment may be paused or discontinued if the study drug is found to be harmful such as development of kidney or hepatic failure or insufficiency as measured by renal and hepatic function labs, respectively. If abnormal values are noted as defined in section 8.1 and no other cause for these laboratory changes are likely, then drug will be stopped, and repeat labs will be obtained at reasonable intervals per investigator's clinical judgement after discontinuation until labs have normalized to stabilized. Treatment may be restarted if labs have returned to baseline using the same ramp up schedule as described for visits 2, 3 and 4.

#### 4.4 Subject Withdrawal Criteria

- Failure of subject to adhere to protocol requirements
  - If a patient is unable to adhere to study procedures, they may be withdrawn from the study by the investigator per investigator discretion.
- Subject decision to withdraw from the study (withdrawal of consent)
  - A patient or patient's family/guardian may withdraw consent at any time and cease administration of study drug or placebo. They may be asked to return for follow up testing to ensure that laboratory values are satisfactory (see schedule of events table (SOE)) and please refer to section 6.10.

### 5 Study Drug

#### 5.1 Description

Name and detailed description of the investigational product(s)

- Acetazolamide is an inhibitor of the enzyme carbonic anhydrase. It is a white to faintly yellowish white crystalline, odorless solid, weakly acidic, very slightly soluble in water and slightly soluble in alcohol. The chemical name for acetazolamide is N-(5-Sulfamoyl-1,3,4-thiadiazol-2-yl)-acetamide. The acetazolamide formulations used in our study will be capsules.

- Acetazolamide 250 mg oral capsules: will be compounded by over-encapsulating acetazolamide 250 mg tablet within a gelatin capsule and filled with lactose powder.
- Placebo (to match Acetazolamide)
  - Placebo capsules: to be compounded by filling empty gelatin capsules with lactose powder to match Acetazolamide capsules.

- If the investigator becomes aware of a likely related or related SAE, based on clinical judgement, the subject may be discontinued from placebo or drug. If an SAE occurs, the investigator will report the SAE to the DSMB. The DSMB will decide whether unblinding is necessary and convey their decision to the local study team, who will then implement the decision.

At Visit 5 (26 weeks) a discussion with the subject regarding whether they would like to proceed into the open label extension with acetazolamide will occur. If continuation is preferred, they will be restarted on dose 1 since we are not certain if they were on treatment or placebo. At subsequent visits after visit 5, acetazolamide will be modified in the same manner as above. If not, then neither drug nor placebo will be given to the patient. As this is an open label continuation, acetazolamide will be dispensed by a clinical pharmacy.

